## **10.2 Measurement Methods**

PET images will be interpreted using the AW software (GE Healthcare) and the location of uptake will be recorded for each patient, blinded to the results of other studies. MR images will be evaluated for detection of areas of abnormal signal or anatomical structures, blinded to the results of PET or other studies.

## **10.3 Measurement Time Points**

Uptake will be evaluated after the scan completion.

### **10.4 Secondary Outcome Measure**

- Secondary Outcome measure: Predictive value of malignancy
- Timeframe: After 1 year clinical follow-up
- Description: The predictive value of Ga- NeoBOMB1 PET/MRI and Ga-PSMA R2 PET/MRI imaging will be evaluated based on biopsy and/or imaging results during 12 month standard clinical follow-up. Outcome will be reported as- percentage of detected lesions that were confirmed to be malignant for each imaging method.

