### **5.3 Details of image analysis**

The PET/MRI scans will be interpreted by ABNM certified Nuclear Medicine physicians and an ABR certified Radiologists. Drs [name], [name], [name], and [name] have significant clinical experience and will be blinded to the participants' medical history and the results of other imaging modalities. Consensus read will be obtained for each scan. Each lesion will be tabulated and a comparison of lesion detection by each scanner will be conducted.

The study team will communicate the results of the scans to the referring (treating) physicians who can decide what to do with the findings, including making treatment decisions.

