### **6.3. Follow-up**

Active subject participation ends after the 24 to 72 hour post-scan Safety Follow-up. Investigators will follow subjects by chart review for 12 months post-scan to record any standard of care biopsies or imaging results. If required by treating physicians for standard of care biopsies, the investigators will assist with identification of lesions that can be biopsied, based on Ga-NeoBOMB1 and/or Ga-PSMA-R2 PET/MRI findings.

If a subject transfers clinical care outside of Stanford Healthcare during the chart review clinical follow-up period, investigators will request permission to contact the treating physician to review medical records.

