#### **11.4 Key variables**

Reference standard: disease status of a lesion will be defined by biopsy of suspicious lesions, when clinically feasible. 12-months clinical follow-up with imaging will be gold standard if biopsy cannot be done.

Test to be evaluated:  $^{68}\text{Ga}$ -NeoBOMB1 and  $^{68}\text{Ga}$ -PSMA R2 positivity will be determined by the operator as uptake more than the adjacent background (malignant) or less (benign). Visual conspicuity against background on the diffusion weighted images and presence of an anatomically corresponding abnormality on the T1w and T2w images are the criteria for detecting a lesion on MRI.

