#### **11.5 Sample size justification**

The following estimate is for a per-lesion analysis. We expect approximately 70% of patients (~35) to have one or more PET-positive findings and approximately 1/3 to be biopsied. Our existing data for  $^{68}\text{Ga}$  PSMA-11 and  $^{68}\text{Ga}$ -RM2 (please see attached publications) indicate no false positive findings based on biopsy. We cannot predict an average number of lesions per patient given small data available to date, but if only half of the positive patients have more than one lesion, this will easily yield 50 lesions. We also expect the sensitivity of MR alone to be roughly 40%, while that of PET to be roughly 60% or more. A sample size of 50 patients will provide 90% power at one-sided 5% error to detect such a difference. Participants who complete only one PET/MRI scan (either due to withdrawal of consent or loss to follow-up) will not be replaced with additional subjects.

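### The secondary predictive value divides confirmed-malignant lesions by all detected lesions, so a lesion without a completed reference standard counts as if it were not malignant and the figure is biased low

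*Combined protocol and SAP*

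**What the plan says.** Section 10.4 is the only secondary outcome. It bases predictive value on "biopsy and/or imaging results during 12 month standard clinical follow-up" and reports it as the "percentage of detected lesions that were confirmed to be malignant for each imaging method". Section 11.4.1 sets the analysis population as all lesions identified on the two PET/MRI scans, with no restriction to verified lesions. Section 11.4.2 lists positive and negative predictive value without a formula.

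The reference standard is in section 11.4. The first choice is biopsy: "disease status of a lesion will be defined by biopsy of suspicious lesions, when clinically feasible". The fallback is imaging: "12-months clinical follow-up with imaging will be gold standard if biopsy cannot be done". Section 10.1 agrees in outline. Neither section says what imaging result makes a lesion malignant, benign or indeterminate.

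Section 6.3 says how this information is obtained: "Investigators will follow subjects by chart review for 12 months post-scan to record any standard of care biopsies or imaging results". Active participation ends with the safety contact a few days after the scan, and the calendar in section 7 shows chart review at 12 months but no follow-up scan. Section 11.5 expects about 35 patients with positive PET findings and "approximately 1/3 to be biopsied". Under section 5.3, scan results go to treating physicians, "who can decide what to do with the findings, including making treatment decisions".

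**The concern.** The numerator needs a completed reference standard and the denominator does not. A lesion can miss the numerator for two quite different reasons: it was shown to be benign, or nobody found out. The stated formula treats both alike. Because verification is left to routine care, some unverified lesions should be expected. There is no category for them.

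At stake is what the published number means. A tracer with no observed false positives could be reported with a predictive value well below 100% only because some lesions were never followed up. A reader could not tell that from genuine false positives. The same report could also contain two different predictive values: one from the section 10.4 formula, and one from section 11.4.2 if the analyst uses the ordinary definition, which needs known disease status.

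**Working it through.** **The plan's own figures.** No expected value, precision or test is stated for the predictive value, so there is nothing to reproduce for this outcome. The one design figure in section 11.5 (90% power, 40% versus 60%, n = 50, one-sided 5%) comes back as 89.3% from a one-sample normal approximation. It has no bearing on this point.

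**Step 1: what the formula estimates.** Let V be the share of detected lesions with a completed reference standard, Pv the malignant share among verified lesions and Pu the malignant share among unverified lesions. Take the reference standard as correct when it is completed.

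- Reported under section 10.4: V × Pv
- True predictive value: V × Pv + (1 − V) × Pu
- Shortfall: (1 − V) × Pu

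The shortfall cannot be negative, and it is zero only if every lesion is verified or no unverified lesion is malignant. If Pv = Pu = P, the reported figure reduces to P × V.

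**Step 2: size over a range.** Inputs: biopsy share 1/3 (section 11.5; it most naturally refers to patients, so applying it to lesions is an assumption); P = 100% (section 11.5 reports no false positives on biopsy, but for PSMA-11 and RM2, which are not the study tracers), with 80% as an alternative; f, the share of unbiopsied lesions resolved by follow-up imaging, which the documents do not give.

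V = 1/3 + (2/3) × f

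| f | V | Reported if P = 100% | Reported if P = 80% |
|---|---|---|---|
| 0.25 | 0.50 | 50% | 40% |
| 0.50 | 0.67 | 67% | 53% |
| 0.75 | 0.83 | 83% | 67% |
| 0.90 | 0.93 | 93% | 75% |
| 1.00 | 1.00 | 100% | 80% |

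**Step 3: the same in counts.** Section 11.5 anticipates 50 lesions. Suppose every verified lesion is malignant.

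- 34 verified: 34/50 = 68% (exact 95% CI 53–80%) as written; 34/34 = 100% (90–100%) with a verified-only denominator.
- 42 verified: 42/50 = 84% (71–93%) as written; 42/42 = 100% (92–100%) verified-only.

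These intervals ignore clustering of lesions within patients.

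**Step 4: the alternative has its own error.** The verified-only value is Pv, so its error is (1 − V) × (Pv − Pu), which is upward if verified lesions are more often malignant. Where Pv is at least Pu, this is smaller than the present shortfall whenever Pu exceeds half of Pv. Example with V = 2/3, Pv = 100%, Pu = 80%: the true value is 0.667 + 0.333 × 0.8 = 93%. The present formula gives 67% and the verified-only one 100%, and bounds of 67% to 100% contain the truth.

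**Step 5: comparison between tracers.** Each patient is planned to have both scans and has one follow-up, so a lesion seen by both tracers has one verification status. Verified fractions can differ only through lesions not shared by both scans. Section 11.3 expects about two-thirds the same findings. If that meant two-thirds of each tracer's lesions (an assumption), the difference in V would be one-third of the difference in verification between the tracer-unique lesions. The documents give no figure for the latter.

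**The case against.** The strongest reply is that the plan does not leave unbiopsied lesions without a standard: section 11.4 sends them to 12-month follow-up with imaging. If that works nearly always, the problem is small; at f = 0.9 the shortfall is 7 points with a true value of 100%. This stands as a limit on size. It does not remove the defect, because the imaging is whatever routine care produces.

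It can also be said that section 10.4 rests on biopsy or imaging results and so implicitly covers only lesions that have them, and that section 11.4.2 names predictive value in its ordinary sense. But the reporting sentence in 10.4 states the denominator, section 11.4.1 matches it, and nothing restricts either. Dropping unverified lesions at analysis would be an undocumented departure. It is fair that the present formula is a conservative lower bound; the trouble is that it is presented as the estimate.

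Three stronger readings are tempting, and the documents do not support them.

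- A reader might infer a predictive value of about 33%, as if only biopsied lesions were ever verified. That sets f = 0 and ignores the imaging fallback.
- A reader might infer a specific false gap between tracers, such as 17 points from verified fractions of 50% and 33%. Those fractions have no source here. With two-thirds of lesions shared, such a gap would need verification of tracer-unique lesions to differ by about 50 points (0.167 / 0.333).
- A reader might infer that lesions treated on the strength of the scan are scored as not malignant. Section 5.3 permits treatment decisions, but no section says how a resolved lesion is scored, and response could be read as confirmation. The gap is real; the coding is not stated.

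**Conclusion.** The point holds. Followed literally, section 10.4 counts every detected lesion without a completed reference standard as if it were not malignant, and no other section supplies a verified-only denominator or an indeterminate category. The direction is downward whenever any unverified lesion is malignant. The size is not known: on the assumptions in step 2 with a true value of 100%, the shortfall runs from 50 points at f = 0.25 to 7 points at f = 0.9 and none at f = 1. The product form also needs equal predictive value in verified and unverified lesions, which is doubtful if more suspicious lesions are biopsied more often. A difference in bias between the tracers is possible through unshared lesions, but its size cannot be derived from the documents.

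This is a descriptive secondary outcome with no threshold or test, and the sample size does not depend on it. It should still be corrected, because the rule as stated changes the reported result.

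**What to change.** In sections 10.4 and 11.4.2:

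- Define predictive value as confirmed-malignant lesions divided by lesions with a completed reference standard (biopsy or 12-month follow-up imaging).
- Report the number of detected lesions verified and unverified for each imaging method.
- Beside the estimate, give bounds with all unverified lesions benign (the present formula) and all malignant.
- State how a lesion that resolves after treatment is scored. It should not automatically count as benign; place it in the not-evaluable group, subject to the same bounds.

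This is wording only, with no added scans, visits or patients. The cost is fewer lesions in the denominator, wider intervals, and possible upward bias if more suspicious lesions are verified more often. That last risk is why the counts and bounds must be shown with the estimate.

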## **11. STATISTICAL CONSIDERATIONS**

### **11.1 Statistical Design**

Prospective single center, single-arm study. Patients will be scanned with Ga-NeoBOMB1 PET/MRI and Ga-PSMA R2 PET/MRI. MRI and PET/MRI scans will each be evaluated separately by two readers.

### **11.2 Randomization**

Patients will be randomized equally between having the Ga-NeoBOMB1 PET/MRI scan done first or the Ga-PSMA R2 PET/MRI.

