## 2.5 Study Design

This is a prospective, single center, single-arm phase II study enrolling 50 participants with biochemically recurrent prostate cancer. All patients will first be seen by a Stanford Cancer Institute physician and then referred if appropriate on clinical grounds to [name] or his colleagues for this study. Eligible participants will undergo baseline assessments at enrollment. The following steps will take place after the participant has signed the written consent (participants will be randomized to have  $^{68}\text{Ga}$ -NeoBOMB1 first followed by  $^{68}\text{Ga}$ -PSMA R2 within 2 weeks or  $^{68}\text{Ga}$ -PSMA R2 first followed by  $^{68}\text{Ga}$ -NeoBOMB1 within 2 weeks [50/50 chance for each schedule]).

1. Participant will be asked to drink 1 to 2 glasses of water before arrival at the clinic
2. Participants will be weighed and vital signs (heart rate, blood pressure, respiratory rate, pulse oxymetry) will be recorded
3. Participant will be injected IV with 150 to 250 MBq of  $^{68}\text{Ga}$ -NeoBOMB1
4. Vital signs (heart rate, blood pressure, respiratory rate, pulse oxymetry) will be recorded after the injection
5. Participant will void immediately prior to the scan
6. Approximately 45 minutes after the radiopharmaceutical IV administration, data acquisition will begin in the pelvic region and move toward the head. First, localizer MRI scans will be performed to define the table positions. After correct positioning of the spatial acquisition windows is ensured, the combined PET/MRI acquisition will be initiated with 3 to 5 table positions at a 4-min acquisition time per table position.
7. Participants will be given a copy of the consent form s/he signed and will be dismissed.
8. Vital signs (heart rate, blood pressure, respiratory rate, pulse oxymetry) will be recorded again at the completion of the study
9. Participants will be contacted at 24 to 72 hours following the scan in order to capture potential occurring Adverse Events.

The same will be repeated for  $^{68}\text{Ga}$ -PSMA R2 (within 2 weeks of  $^{68}\text{Ga}$ -NeoBOMB1):

1. Participant will be asked to drink 1 to 2 glasses of water before arrival at the clinic
2. Participants will be weighed and vital signs (heart rate, blood pressure, respiratory rate, pulse oxymetry) will be recorded
3. Participant will be injected IV with 150 to 250 MBq of  $^{68}\text{Ga}$ -PSMA R2

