### **5.2 Details of Imaging (ie, dynamic, static, number of scans, etc.)**

A localizer MRI scan will be performed at 45 minutes after injection of 150 to 250 MBq of Ga-NeoBOMB1 (or Ga-PSMA R2, depending on randomization) to define the table positions. After correct positioning of the spatial acquisition windows is ensured, the combined PET/MRI acquisition will be initiated with 3–5 table positions at a 4-min acquisition time per table position. A volumetric T1 acquisition with fat-water separation and motion correction to enable free-breathing will be obtained at each table position and used for the generation of attenuation maps and for anatomic allocation of the PET results. Simultaneously with the start of the T1 MRI sequence, the PET acquisition will start at the same table position, thus ensuring optimal temporal and regional correspondence between MRI and PET data. The PET acquisition time will be 4 min per table position, taking delayed acquisition times and radioactive decay into account. As the T1 will take less than 4\ minutes, a rapid diffusion weighted MRI will also be performed. After completion of the PET acquisition, the table will be moved to the next table position and the procedure will be repeated. Upon completion of the PET acquisition for all stations, volumetric post-contrast T1- and T2-weighted MR images may be obtained at multiple stations as needed.

A localizer MRI scan will be performed at 45 minutes after injection of 150 – 250 MBq of Ga-PSMA R2 (or Ga-NeoBOMB1, depending on randomization) to define the table positions. After correct positioning of the spatial acquisition windows is ensured, the combined PET/MRI acquisition will be initiated with 3–5 table positions at a 4-min acquisition time per table position. ----Only MR sequences required for attenuation correction of PET data will be acquired.

Participants will be randomized to have Ga-NeoBOMB1 first followed by Ga-PSMA R2 within 2 weeks or Ga-PSMA R2 first followed by Ga-NeoBOMB1 within 2 weeks (50/50 chance for each schedule).

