##### **11.4.2 Analysis Plan**

- Sensitivity, specificity, and positive and negative predictive value of imaging modalities will be estimated.
- Sensitivity and specificity of PET/MRI and MR alone will be compared by McNemar tests of paired proportions.
- The number and type of discrepancies between  $^{68}\text{Ga}$ -NeoBOMB1 and  $^{68}\text{Ga}$ -PSMA R2 will be tabulated.
- We will explore hypotheses about the reasons for such discrepancies, such as PSA level/velocity, Gleason score, and location.

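### Scan order is randomised but no planned analysis uses it: reconcile sections 2.5 and 5.2 on MR content, then tabulate tracer discrepancies by order

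*Combined protocol and SAP*

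**What the plan says.** Sections 2.5, 5.2 and 11.2 all randomise the order of the two scans, which are to be done within 2 weeks of each other. Section 2.5 gives a "50/50 chance for each schedule", and section 11.2 says "Patients will be randomized equally between having the" NeoBOMB1 scan or the PSMA R2 scan first. No block size or other balancing method is given.

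The one named test in section 11.4.2 is for PET/MRI against MR: "Sensitivity and specificity of PET/MRI and MR alone will be compared by McNemar tests of paired proportions". For tracer against tracer, the same section says "The number and type of discrepancies between" the two will be tabulated, and it names PSA level or velocity, Gleason score and location as examples of reasons to explore. Section 10.1 compares lesion counts and names no test. Order, period and sequence appear in none of sections 10.1, 10.4, 11.3 and 11.4.2.

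On MR content, section 5.2 describes one scan with T1, adds that "a rapid diffusion weighted MRI will also be performed", and says that "volumetric post-contrast T1- and T2-weighted MR images may be obtained at multiple stations as needed". For the other scan it says "Only MR sequences required for attenuation correction of PET data will be acquired". Each paragraph notes that the tracers may swap according to the randomisation. Section 2.5 carries the same restriction in the PSMA R2 steps only, and section 6.2 refers to section 2.5 for how imaging is done.

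Section 11.5 says that participants with only one scan "will not be replaced with additional subjects".

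**The concern.** A randomised order is useful only if the analysis looks at it. If the first scan has richer MR than the second, some tracer discrepancies may reflect which scan came first and not which ligand was injected. A single table over both orders cannot separate the two. Those discrepancies are what section 11.4.2 sets out to explain, and section 11.3 judges agreement between the tracers from the first 20 participants. Because incomplete pairs are not replaced, the two orders need not be equal in size among completers, so an order effect may not cancel exactly.

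**Working it through.** **1. The plan's own figure.** Section 11.5 states 90% power for sensitivity of 40% (MR) against 60% (PET) with 50 patients, one-sided 5%. A one-sample normal approximation gives Φ[(0.20 × √50 − 1.645 × √0.24) / √0.24] = Φ(1.24) = 89.3%, which reproduces it. A paired McNemar calculation gives 90% only if discordance is about 0.25. Neither version involves scan order, so nothing below changes this figure.

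**2. MR content, side by side.**

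| Section | Fuller MR | Attenuation-correction MR only | MR content follows |
|---|---|---|---|
| 5.2 | scan described first, either tracer | scan described second, either tracer | order |
| 2.5 | no restriction in the NeoBOMB1 steps | stated in the PSMA R2 steps | tracer |

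Both cannot describe a participant who has PSMA R2 first. Steps 3 to 6 take the section 5.2 reading.

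**3. Net tracer difference.** Let τ be the true difference (NeoBOMB1 minus PSMA R2) and π an additive advantage of the first scan. The expected difference is τ + π in the n1 participants who have NeoBOMB1 first and τ − π in the n2 who have PSMA R2 first. Ignoring order gives τ + π(n1 − n2)/(n1 + n2). The mean of the two within-order differences gives τ. The documents give no value for π, so a range is shown.

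| Completers by order | (n1 − n2)/N | π = 5 points | π = 10 | π = 20 |
|---|---|---|---|---|
| 25/25 | 0 | 0 | 0 | 0 |
| 28/22 | 0.12 | 0.6 | 1.2 | 2.4 |
| 30/20 | 0.20 | 1.0 | 2.0 | 4.0 |

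If allocation were an unrestricted coin toss for 50 participants, the chance of 28/22 or worse is 48%, and of 30/20 or worse 20%. Blocked allocation would make both smaller before dropout.

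**4. Discrepancies.** Take discordance of 1/3 (section 11.3), τ = 0, 25 per order and an assumed π of 16 points. In each order the discordant pairs that favour the first scan number 25 × (1/3 + 0.16)/2 = 6.2, and those that favour the second 25 × (1/3 − 0.16)/2 = 2.2. By order, the table reads 6.2 to 2.2 for NeoBOMB1 when it goes first and 2.2 to 6.2 when it goes second. Over both orders it reads 8.3 to 8.3, and the order effect cannot be seen.

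The total count need not rise much. In simulations with existing discordance near 1/3, it was 34.4% with no order effect and 34.0%, 34.3% and 36.1% with effects of 8, 16 and 28 points. It rises most where the tracers would otherwise agree. If they agreed in everyone and MR content alone changed the findings in 5%, 10% or 20% of participants, the chance that all 20 interim participants show the same findings would be 0.95^20 = 36%, 0.90^20 = 12% or 0.80^20 = 1%.

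**5. Standard error at balance.** Ignoring order, it is √[(1/3)/50] = 0.082. Stratified with π = 0.16, it is √[(1/3 − 0.0256)/50] = 0.078. The ratio is 1.04.

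**6. Error rates if the tracers were tested** (simulated, no tracer difference, two-sided 5%). At 25/25 the mean unstratified difference was within 0.001 of zero, and McNemar rejected in 4.6%, 4.3% and 2.9% for order effects of 8, 16 and 28 points. At 30/20 with the extreme 28-point effect, the bias was 5.6 points and rejection 7.5%, against 0.1 points and 5.8% for a stratified z test. With no order effect, the stratified z test rejected in 5.5% to 5.8% and McNemar in 5.0% to 5.3%.

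**The case against.** The strongest reply is that randomising the order already does the work. With equal orders an additive effect cancels, and the residuals in step 3 are small beside a standard error of about 8 points. That stands for the net difference. It does not answer step 4, because the plan tabulates individual discrepancies and these do not cancel.

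A second reply is that extra MR may hardly touch tracer positivity. Section 11.4 defines positivity by uptake above adjacent background, and section 10.2 has PET and MR read blinded to each other. This also largely stands. The 16 points come from counting a lesion if either PET or MR sees it, with independent reads: 1 − 0.6 × 0.4 = 0.76, less 0.60. The documents do not support that as an estimate. Some influence remains possible, since sections 5.3 and 10.1 speak of lesions on PET/MRI and section 5.2 uses the T1 images for anatomic allocation.

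A third reply is that no planned inference depends on order. The only named test and the power statement concern PET against MR, the tracer table is descriptive, and its list of explanations is open-ended. That is correct and limits the weight of the point. The interim rule in section 11.3 is all-or-none, so there is no paired test there to stratify.

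**Conclusion.** The point holds as a low-cost improvement to the analysis, together with a contradiction that must be resolved. Scan order is randomised and used nowhere, and the table in section 11.4.2 as planned cannot tell first-scan discrepancies from tracer discrepancies. If MR content follows order, the residual in the net difference is 0.6 to 4.0 points over the assumed effects and splits in step 3, and zero at balance. The standard error is about 4% too wide at an assumed 16 points. All order-effect sizes and splits are assumptions.

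A reader might infer three stronger things that the documents do not support:

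- That ignoring order biases the tracer comparison as such. With equal orders it does not, and the unstratified test is slightly conservative.
- That a first-scan advantage is an established feature of the design. Section 5.2 alone suggests it, and section 2.5 ties the reduced MR to PSMA R2. On that reading MR content is confounded with tracer, and order stratification removes none of the difference.
- That stratification removes every order effect. It handles an additive one only, not carry-over or a tracer-by-order interaction.

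**What to change.** 1. Reconcile sections 2.5 and 5.2 so that both state whether MR content follows scan order or tracer. If it follows tracer, say in section 11.4.2 that tracer differences include a difference in MR content that order cannot adjust for.
2. In section 11.4.2, present the NeoBOMB1/PSMA R2 discrepancy table separately by randomised order, with the number of complete pairs in each.
3. Show the same table by order at the 20-participant look, as a descriptive aid only.
4. If a tracer-versus-tracer comparison is made, stratify it by order. At patient level, the mean of the two within-order differences or an exact Mainland-Gart test would serve. At lesion level, the method must also account for several lesions per patient.

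The cost is a few sentences and a little more analysis, since order is known for every participant. Interim cells will be sparse: 20 × 1/3 is about 7 discordant participants over two orders. The choice of method also matters. With a true tracer difference simulated at 25/25 (observed mean 12.5 points) and a 26-point order effect, the large-sample Mainland-Gart test rejected in 24%, McNemar in 31% and the stratified difference in 41%. Sample size and the stated power do not change.
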